## 5 ANALYSIS SETS

#### 5.1 Intent-to-Treat Population

The Intent-to-Treat (ITT) population is defined as all subjects who were randomized in this study. The ITT population will be analyzed by treatment arm as randomized, (i.e., treatment arm by randomization assignment) regardless of whether or not study drug was administered. The ITT population will be used to conduct efficacy analyses, unless otherwise specified.

#### **5.2** Safety Population

The safety (SAF) population is defined as all randomized subjects who received at least 1 dose of study drug. The safety population will be used to conduct safety analyses by treatment arm as treated (i.e., based on the actual study drug the subject mostly received, rather than the study drug to which the subject was randomized to).

Detailed criteria for analysis sets will be laid out in Classification Specifications (CS) and the allocation of subjects to analysis sets will be determined prior to database hard lock. This was done prior to unblinding.

## 6 ANALYSIS VARIABLES

Analysis variables are defined in the SAP for the primary analysis. This section further details those for which data derivation require to be modified.

#### 6.1 Overall Survival

OS is defined as the time from randomization to death from any cause. All deaths on or before the data cut-off will be included.

For patients who are alive at the time of the cut-off date, OS time will be censored on the last date the patient is known to be alive or the cut-off date, whichever occurs first. The date the patient is last known alive by the cut-off date will be derived as follows:

- for patients on treatment by the cut-off date (i.e., patients who did not discontinue from treatment), the date last known alive will be the cut-off date.
- for patients who withdraw consent by the cut-off date, the date last known alive is the date of consent withdrawal.
- for patients lost to follow up, the date last known alive depends on the period the patient was lost to follow-up. It will be as follows:

Period lost to follow-up	The date last known alive		
Since randomization (i.e. without	The date of randomization		
further post-randomization visit)			
During treatment period	The last assessment/visit date or the date of the last		
	dose of study drug, whichever occurs later		
Safety follow-up period	The date of the last dose of study drug or the last		
	treatment visit date collected on the End of Treatment		
	Case Report Form (CRF) page, whichever occurs last.		
Long-term follow-up period	The last visit/contact date (collected either on the		
	30 Day Follow-Up Status CRF page, or the Patient		
	Status - Survival CRF page or the Long-Term Follow-		
	Up Status CRF page).		

• for other patients (i.e., not on treatment, not withdrawn and not lost to follow-up) who are alive by the cut-off date, the date last known alive is the date of last visit (collected either on the Patient Status - Survival CRF page or the Long-Term Follow-Up Status CRF page) or the date of randomization, whichever occurs last.

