## **Study Design Overview:**

This is a multinational phase 3, randomized, double-blind, placebo-controlled efficacy and safety study of enzalutamide plus ADT versus placebo plus ADT in subjects with mHSPC.

Approximately 1100 subjects will be randomized centrally 1:1, and the randomization will be stratified by volume of disease (low versus high) and prior docetaxel therapy for prostate cancer (no prior docetaxel, 1-5 cycles, 6 cycles). High volume of disease is defined as metastases involving the viscera or, in the absence of visceral lesions, there must be 4 or more bone lesions, at least 1 of which must be in a bony structure beyond the vertebral column and pelvic bone. Prior docetaxel therapy is defined as 1 or more cycles of docetaxel but no more than 6 cycles.

Study drug therapy should be continued as long as the subject is tolerating the study drug and continues ADT until radiographic disease progression is documented as outlined in the table below or starting an investigational agent or new therapy for treatment of prostate cancer. It is recommended that subjects remain on study treatment until radiographic progression is confirmed by independent central imaging review. Subjects who discontinue study treatment without radiographic progression will continue to follow the radiographic assessment schedule until radiographic progression event is confirmed by the central imaging independent reviewer or until the target number of progression events is reached as assessed by the central review. All subjects will be followed until death to assess for OS. Once the final number of events has been reached to trigger the final OS analysis, survival follow-up will be considered complete and subjects will be discontinued from long term follow-up. Study films (computed tomography [CT]/magnetic resonance imaging [MRI] and bone scan) should be read on site and also be submitted in digital format to the Sponsor-designated facility for independent central review. Each site should ideally designate the same reader who will evaluate the images for any one subject for the duration of the trial.

Radiographic disease progression is defined by Response Evaluation Criteria in Solid Tumors (RECIST) version 1.1 for soft tissue disease or the appearance of 2 or more new lesions on bone scan. The documentation and confirmation required for the determination of radiographic progression is listed in the following table.

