#### 12.6.2 Schedule and Assessments

For procedures see Table 4 (Open-Label Extension Schedule of Assessments).

Subjects treated with enzalutamide during the double-blind period will sign informed consent on Open-Label Day 1 and are required to return for study visits every 12 weeks (see Figure 3 Open-Label Extension schematic). Subjects treated with placebo during the double-blind period will sign informed consent at the Open-Label Day 1 visit after which they will be switched to enzalutamide (dosing below); these subjects will be required to return for study visits at Open-Label Week 5 (Day 29), Week 13 and every subsequent 12 weeks. All Open-Label Day 1 visits should occur within approximately 16 weeks after the approval and activation of this protocol amendment at the study site.

Subjects will take enzalutamide as four 40-mg soft gelatin capsules (160 mg/day) by mouth once daily with or without food. Subjects treated with enzalutamide during the double-blind period and dosed at a lower daily dose may continue at the lower dose as appropriate.

Study assessments will include safety evaluations including AEs, concomitant medications, clinical laboratory tests, brief physical examinations, ECGs and vital signs. Radiographic assessments (CT/MRI and bone scan) will be performed as per the Open-Label Extension Schedule of Assessments [Table 4] until the subject progresses radiographically based on local assessment and/or meets other treatment discontinuation criteria [Section 12.6.6 Duration of Treatment and Criteria for Discontinuation].

EudraCT number 2015-003869-28

- CONFIDENTIAL -

Subjects are to have a safety follow-up 30 days after the last dose of open-label enzalutamide. If a new antineoplastic or investigational anticancer treatment is started before 30 days after the last dose of open-label enzalutamide, then safety follow-up should occur immediately before starting the new treatment.

[figure not shown]
Long-term follow-up data will be collected every 12 weeks until the completion of OS analysis. The information collected will include survival status, new antineoplastic therapies for prostate cancer, skeletal-related events and associated interventions.

Sponsor: APGD ISN/Protocol 9785-CL-0335

EudraCT number 2015-003869-28 - CONFIDENTIAL -

- CONFIDENTIAL -

Figure 3 Schematic – Open-Label Extension

\* Week 5 visit required only for subjects previously receiving placebo.

EudraCT number 2015-003869-28

- CONFIDENTIAL -

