**Table 4** Open-Label Extension Schedule of Assessments

Study Period or Visit	OL Treatment 			Unscheduled Visit	OL Safety Follow-up	OL Long Term Follow-up 
Study Week	OL 1  (Day 1)	OL 5  (Day 29)	OL 13 and Every Subsequent 12 Weeks (Day 85 and Every Subsequent 84 Days)	Varies 	30 Days after Last Dose 	Every 12 Weeks
Window (Days)	NA	± 3	± 5	NA	± 7	± 7
Informed Consent 	X					
Inclusion/Exclusion for OLE	X					
Open-Label Enrollment (via IRT)	X					
Brief Physical Examination	X		X	X	X	
Vital Signs including Weight	X	X	X	X	X	
ECOG Performance Status	X	X	X	X	X	
12-lead Electrocardiogram	X				X	
Clinical Labs	X	X	X	X	X	
Sample for Mutation Analysis 	X		$X^8$			
Radiographic Assessments 	X 		X			
QoL Assessment (QLQ-PR25, EQ-5D-5L, FACT-P, Brief Pain Inventory-Short Form)	X		X		X	X 
Adverse Events 	X	X	X	X	X	
Concomitant Medication Review	X	X	X	X	X	
Study Drug Dispensing (via IRT)	X	X	X			
Study Drug Accountability	X	X	X		X	
Long-Term Follow-up Assessments 						X

ECOG: Eastern Cooperative Oncology Group; EQ-5D-5L: EuroQol Group-5 Dimension-5 Level Instrument; FACT-P: Functional Assessment of Cancer Therapy-Prostate; IRT: Interactive Response Technology; NA: not applicable; OL: Open-Label; OLE: Open-Label Extension; QLQ-PR25: Quality of Life Prostate-specific Questionnaire; QoL: Quality of Life.

Footnotes continued on next page

Sponsor: APGD ISN/Protocol 9785-CL-0335

EudraCT number 2015-003869-28 - CONFIDENTIAL -

- Subjects continuing into the Open-Label (OL) extension period may be asked to complete their extension period participation in another Astellas-sponsored study upon activation of the roll-over extension study. An OL 30-day follow-up visit is not required for subjects who choose to participate in the other Astellas-sponsored study.
- 2 Long-term follow-up assessments include survival status, symptomatic skeletal events and new antineoplastic therapies for prostate cancer. May be obtained by telephone contact, chart review or clinic visit. This assessment will be collected until death, withdrawal of consent, final OS analysis or study termination.

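### SAP 6.1 ends follow-up at different dates for on-treatment and off-treatment survivors, which can slightly bias the confirmatory OS hazard ratio

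*SAP*

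**What the plan says.** SAP 6.1 sets the OS censoring date by treatment status.

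- On treatment, meaning "patients who did not discontinue from treatment), the date last known alive will be the cut-off date".
- Off treatment, not withdrawn and not lost: for those "alive by the cut-off date, the date last known alive is the date of last visit", taken from the survival or long-term follow-up CRF page (or the randomization date, if later).
- Deaths: "All deaths on or before the data cut-off will be included".

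Withdrawn and lost subjects have their own rules, which are not at issue here.

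Both groups are seen at the same interval. Off treatment, Protocol 12.6.2 states: "Long-term follow-up data will be collected every 12 weeks until the completion of OS analysis". On open-label treatment, the visit column in Protocol Table 4 reads "OL 13 and Every Subsequent 12 Weeks (Day 85 and Every Subsequent 84 Days". The footnotes to Protocol Table 1 say that extra follow-up contacts may be requested; nothing requires a survival check at the cut-off.

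The OS sensitivity analyses in SAP 7.4.1 address crossover, COVID-19 deaths and a piecewise hazard ratio. None varies the censoring date.

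**The concern.** An off-treatment subject who survives leaves the risk set at his last contact, up to about 12 weeks before the cut-off. If he dies in those same weeks and the death is known, he stays at risk until death and counts as an event. Off-treatment follow-up near the cut-off is therefore kept when it ends in death and dropped when it does not. On-treatment survivors are kept to the cut-off, although their visits are also 12 weeks apart.

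If the arms have different shares of survivors off treatment, the apparent hazard is inflated more in one arm than in the other, even when true survival is the same. Final OS at two-sided 0.04 is the only formal test in this SAP: time to new antineoplastic therapy is analysed without one (SAP 7.4.2).

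**Working it through.** **Inputs from the documents.** About 1100 subjects, 1:1 (SAP 3.2). 342 deaths, HR 0.73, 80% power, medians of 40 and 55 months, exponential survival (SAP 4). Two-sided 0.04 (SAP 7.4.1). Contacts every 12 weeks (Protocol 12.6.2).

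**Assumptions, not in the documents.** Share of survivors off treatment in each arm; gap from last contact to cut-off uniform over 0 to 12 weeks; treatment status independent of death risk; all deaths to the cut-off known unless stated; accrual 24 months; unstratified analysis.

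**1. The plan's own figure.** Schoenfeld: 4 × (2.054 + 0.842)² / (ln 0.73)² = 339 deaths. Freedman: 345. With 342 deaths, power is 80.4%. The planned 342 reproduces.

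**2. Hand approximation with no true effect.** Per arm: 342/2 = 171 deaths and 550 − 171 = 379 survivors. The mean gap is 6 weeks, or 42/30.4375 = 1.38 months. Person-time is PT = 171/λ. With λ = ln 2/40 = 0.01733, PT = 9,868 months. Let p0 and p1 be the off-treatment shares of survivors on placebo and enzalutamide. Then

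HR ratio ≈ (1 − p0 × 379 × 1.38/PT) / (1 − p1 × 379 × 1.38/PT).

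- 60%/40%: (1 − 0.0318)/(1 − 0.0212) = 0.989.
- 80%/40%: (1 − 0.0424)/(1 − 0.0212) = 0.978.

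**3. Simulation.** Cut-off at the 342nd death, control median 40 months. Cox HR under the SAP rule, compared with censoring every survivor at the cut-off:

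| Off treatment, placebo/enzalutamide | Change in HR, true HR 0.73 | Change in HR, true HR 1 |
|---|---|---|
| 40%/40% | 0.0% | 0.0% |
| 50%/40% | −0.5% | −0.6% |
| 60%/40% | −1.0% | −1.2% |
| 80%/40% | −2.0% | −2.4% |
| 40%/60% | +1.0% | +1.2% |
| 100%/0% (bound) | −5.0% | −5.7% |

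The hand figures agree. Accrual of 12 or 36 months gives −1.1% or −1.0% at 60%/40% with true HR 0.73.

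**4. Error rate.** The standard error of log HR is 2/√342 = 0.108, and the critical value is 2.054. A −1.17% shift is 0.0117/0.108 = 0.108 standard errors, so the chance of a false claim for enzalutamide is Φ(−2.054 + 0.108) = 0.026, against a nominal 0.020. Simulated values are 0.026 at 60%/40% and 0.034 at 80%/40%.

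**5. Calendar time.** The planned start is 1Q2016 (Protocol synopsis). The SAP is dated 18 July 2021 and still treats the 342-death analysis as future, so a cut-off near 64 months is more realistic than the 34 to 37 months in step 3. With an assumed 20-month accrual, mean potential follow-up is about 54 months, 342/1100 = 0.311, and λ = −ln(1 − 0.311)/54 = 0.0069. Then PT = 171/0.0069 = 24,783 months.

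- 60%/40%: (1 − 0.0127)/(1 − 0.0084) = 0.996.
- 80%/40%: (1 − 0.0169)/(1 − 0.0084) = 0.991.

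Simulation at this timing gave ratios of 0.989 to 0.997. An intermediate case (true HR 0.73, control median 70 months, cut-off about 56 months) gave −0.6% at 60%/40% and −1.2% at 80%/40%.

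**6. What removes the effect** (60%/40%, true HR 0.73, timing of step 3).

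- Last contact within 2 weeks of the cut-off: −0.15%.
- Off-treatment deaths after the last contact all missed: +0.1%; half missed: −0.5%.
- In separate runs, one censoring rule for all survivors returned the ratio to 1.000 in every scenario.

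**The case against.** A reader might infer that the rule does bias the OS hazard ratio toward enzalutamide. The documents do not support that.

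- **Shares.** The sign follows the arm with more off-treatment survivors, and no shares are given. Placebo subjects may cross over to open-label enzalutamide (Protocol 12.6.1), including some who progressed radiographically but stayed on drug (note to the second exclusion in Protocol 12.6.4). Those still on drug would fall under the on-treatment bullet, which narrows the gap.
- **Ascertainment.** The shift needs deaths after the last contact to be known. The sentence on deaths in SAP 6.1 is a counting rule, not evidence that they are found. Missed deaths remove the effect.

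A reader might also infer that a closing survival check is ruled out, because the synopsis says "Once the final number of events has been reached to trigger the final OS analysis, survival follow-up will be considered complete". That sentence does not exclude one. Extra contacts are permitted, and SAP 6.1 censors at the earlier of last known alive and the cut-off, which contemplates contacts after it. However, SAP 7.1 limits reported data to visits on or before the cut-off, so such contacts have no clear place in the derivation.

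Nor is on-treatment survival at the cut-off a bare guess. Fatal adverse events are reported within 24 hours of awareness (Protocol 5.5.5), and subjects lost during treatment are censored under their own rule.

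These points limit direction and size; the asymmetry itself remains. There is also some support for the expected sign. Protocol 1.4 reports longer rPFS and later new therapy on enzalutamide, and both events are routes off treatment. Discontinuations for adverse events were similar in the pooled phase 3 data (17.2% versus 16.1%, Protocol 1.3). The open-label exclusions keep some former placebo subjects off drug. Protocol 2.2.1 has sites collect secondary contacts to establish survival status, so many late deaths should be found.

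**Conclusion.** The two censoring dates differ as described, and the difference depends on a post-randomization status. The OS hazard ratio can be slightly biased as a result, probably toward enzalutamide if more placebo survivors are off treatment.

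For assumed differences of about 10 to 45 points among survivors and a uniform 0 to 12 week gap, the shift is roughly 0.3% to 2%. With a cut-off near 64 months it is about 0.3% to 1%; a ratio of 0.991 there gives a false-claim rate for enzalutamide of about 2.4% instead of 2.0%. This would matter only for a result close to the 0.04 boundary.

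The figures rest on assumed shares, full capture of deaths after the last contact, and off-treatment status unrelated to death risk. None of these can be checked from the documents. The case for acting is that this is the SAP's one formal test, no planned sensitivity analysis would show the problem, and the correction is cheap.

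**What to change.** In SAP 6.1, replace the on-treatment bullet and the final bullet with one rule for all survivors who are not withdrawn or lost, whatever their treatment status.

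- **Preferred.** Update survival status for every living subject at the cut-off and censor all of them there. State that a contact dated on or after the cut-off may be used to confirm this, given the data limit in SAP 7.1. Cost: one round of status contacts, which the protocol already permits.
- **Otherwise.** Censor every such survivor at the last documented alive date on or before the cut-off. Cost: a small derivation change and a few weeks of follow-up lost for on-treatment survivors; no new data. This is second best because later deaths still count, so the same distortion then applies to both arms. It cancels in the hazard ratio but slightly lowers both survival curves.
- **Minimum.** Keep the present rule and add an OS sensitivity analysis in SAP 7.4.1 with one common censoring rule, reporting the off-treatment share of survivors by arm. Cost: one extra run.

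SAP section 1 allows revision before database hard lock.

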# 12.6.1 Rationale

Following unblinding at the end of the double-blind period and demonstration of a statistically significant advantage of enzalutamide over placebo when added to ADT, as assessed by the primary endpoint, all eligible subjects may be treated on study with open-label enzalutamide at the discretion of the subject and investigator.

Day 1 of the open-label extension will occur after consent is signed and eligibility is confirmed. Treatment with open-label enzalutamide will be stopped upon disease progression when, in the opinion of the investigator, there is no added clinical benefit to continue treatment with enzalutamide, and/or when discontinuation criteria are met [Section 12.6.6 Duration of Treatment and Criteria for Discontinuation].

Subjects who do not participate in the open-label extension or who withdraw consent for further treatment will discontinue study treatment and return for a 30-day safety follow-up visit as per protocol. Long-term follow-up assessments will be completed as per protocol.

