#### 12.6.6 Duration of Treatment and Criteria for Discontinuation

Open-label enzalutamide administration may continue as long as the investigator considers treatment to be beneficial or until any of the following discontinuation criteria are met:

- Any AE that is intolerable to the subject and which cannot be ameliorated by adequate
  medical intervention and/or dose reduction or that in the opinion of the investigator or
  medical monitor would lead to undue risk if enzalutamide continues.
- Seizure or any condition that significantly predisposes the subject to seizure such as brain metastasis or clinically evident stroke.
- Confirmed event of PRES by brain imaging, preferably MRI.
- Initiation of investigational agent or new therapy for prostate cancer.
- Gross noncompliance with protocol procedures and/or enzalutamide study drug management.
- Withdrawal of consent by subject for any reason. Subject may withdraw consent for
  further treatment with enzalutamide study drug, but may still participate in the long-term
  follow-up assessments. Specific details of procedures declined or allowed should be
  documented by study staff.
- Subject is lost to follow-up despite reasonable efforts by the investigator to contact
  subject to complete study related assessments, record outstanding data and retrieve
  enzalutamide study drug. Following unsuccessful telephone contact, an effort should be
  made to contact the subject by mail using a method that provides proof of receipt.
  Alternate contacts are permissible if subject is not reachable and allowed by local
  guidelines.
  - Study termination by sponsor.
- Completion of final OS analysis.
- Death.

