#### Sponsor: Astellas Pharma Global Development, Inc

ISN/Protocol 9785-CL-0335

- ‡ After study drug discontinuation, all patients MUST undergo long term follow-up. Long term follow-up assessments will include monitoring for survival status, new antineoplastic therapies for prostate cancer, and symptomatic skeletal events. Follow-up may be conducted by telephone interview. Patients will continue to be scanned every 12 weeks until radiographic progression is confirmed by independent review or the number of radiographic progression-free survival events is reached. For patients continuing with radiographic assessments, if seen in clinic, QoL assessment will also be completed until the initiation of new antineoplastic therapy for prostate cancer or the number of progression events is reached. Additional follow-up contacts may be requested. Patients will be followed for overall survival until death, lost to follow up, overall survival final analysis or termination of the study by the sponsor.
- § Or prior to initiation of new antineoplastic therapy for prostate cancer, whichever occurs first.
- A brief physical examination is required at each visit, with the exception of the screening visit during which a complete physical examination will be completed.
- †† Laboratory assessments include serum chemistries and hematology.
- ‡‡ Genotyping samples will only be collected from patients who agree to provide genotyping samples as documented by signing a separate genotyping informed consent form (ICF).

CCI

- ∬
- §§ The abdominal-pelvic CT scan or MRI, bone scan, chest x-ray or chest CT must occur within 6 weeks of day 1; otherwise the screening visit assessment must be repeated. Radiographic assessments performed prior to informed consent, as part of the routine care, may be used as the baseline assessment if performed within 6 weeks of day 1 and if digital format images are available for submission to the sponsor-designated independent central review facility.
- The window for all radiographic (CT/MRI) assessments is ± 7 days. For patients who discontinue study treatment without radiographic progression, confirmed by central review, patients will continue to be scanned every 12 weeks until radiographic progression is confirmed by independent review or the number of radiographic progression-free survival events is reached.
- ††† Chest CT is required at all imaging time points if screening chest x-ray demonstrates metastatic chest disease.

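### Does the unqualified consent-withdrawal rule in SAP 6.1 bias the final overall survival analysis?

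*SAP*

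**What the plan says.** SAP 6.1 has an event rule, a general censoring rule and a list of special cases.

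- Events: "All deaths on or before the data cut-off will be included".
- General censoring: a patient alive at the cut-off is censored at the latest date of known survival, or at the cut-off if that is earlier.
- Withdrawal: "for patients who withdraw consent by the cut-off date, the date last known alive is the date of consent withdrawal".
- The rule that uses later survival contacts is limited to one group: "for other patients (i.e., not on treatment, not withdrawn and not lost to follow-up) who are alive by the cut-off date".

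The protocol knows more than one kind of withdrawal. Section 6.1 lists withdrawal from the study among the reasons to stop drug, and withdrawal from further follow-up among the reasons to stop follow-up. Section 12.6.1 says "Subjects who do not participate in the open-label extension or who withdraw consent for further treatment will discontinue study treatment", and then "Long-term follow-up assessments will be completed as per protocol". Section 12.6.6, under "Withdrawal of consent by subject for any reason", says a subject may withdraw consent for "further treatment with enzalutamide study drug, but may still participate in the long-term" follow-up. The long-term follow-up footnote to SAP Table 1 adds "After study drug discontinuation, all patients MUST undergo long term follow-up".

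**The concern.** A subject who withdraws from treatment only can have a consent-withdrawal date and, after it, survival contacts every 12 weeks. SAP 6.1 does not say which governs. Let W be the withdrawal time, L the last contact and D the death time, with W before L and D. If the withdrawal bullet covers this subject:

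- dies before cut-off: event at D;
- alive at cut-off: censored at W, and L − W is discarded.

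Censoring would then depend on the outcome. Deaths stay in and survivors' known time drops out, so the hazard is overstated in whichever arm has more such withdrawals. The derivation feeds the stratified log-rank test and Cox hazard ratio of the final OS analysis at 2-sided 0.04, and treatment codes are already open. An unclear rule for this endpoint deserves a check.

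**Working it through.** **1. The plan's own figure.** Inputs from SAP section 4 and 7.4.1: hazard ratio 0.73, 80% power, 2-sided 0.04, 1:1 allocation.

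- Schoenfeld: 4(2.054 + 0.842)² / (ln 0.73)² = 339 deaths.
- Freedman: (1.73/0.27)² × (2.054 + 0.842)² = 345 deaths.
- Power with 342 deaths (Schoenfeld): 80.4%.

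The stated 342 is reproduced. At 342 deaths the standard error of the log hazard ratio is about 2/√342 = 0.108, and the critical hazard ratio is exp(−2.054 × 0.108) = 0.80.

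**2. Which withdrawal is meant.**

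| Place | Bearing on the reading |
|---|---|
| SAP 3.2; Protocol synopsis, 2.2.1, footnote 2 of Tables 4 and 5 | Consent withdrawal, unqualified, is an end point of survival follow-up |
| SAP 6.1, general censoring sentence | Aim is the last date of known survival |
| SAP 6.1, last bullet | Off treatment, withdrawn and lost to follow-up are three separate statuses |
| SAP 7.2.1 | Treatment, 30-day and long-term follow-up discontinuation are tabulated separately by reason |
| Protocol 12.6.6 | Staff must record which procedures the subject declines or still allows |
| Protocol and SAP Table 1 footnotes | Lists of what ends OS follow-up omit withdrawal; they do not say that follow-up continues after it |

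The SAP's own use of the term is withdrawal from survival follow-up. A treatment-only withdrawer is then off treatment but not withdrawn, falls under the last bullet, and is censored at last contact. The records needed to tell the two kinds apart are planned.

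**3. Size if it were coded the other way.** Simulation under a true hazard ratio of 1:

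- 550 per arm, exponential survival, cut-off at the 342nd recorded death, unstratified log-rank test, nominal 2% false claims for enzalutamide.
- Assumed, not in the documents: uniform 22-month accrual; unblinding 3 months after the 84th death (the 84 is from SAP 7.4.1); withdrawals spread over the next 24 months; all later deaths of treatment-only withdrawers recorded; all withdrawal rates.
- 16,000 runs or more per setting. All withdrawals are treatment-only unless stated.

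| Median OS | Placebo vs enzalutamide withdrawal | Estimated HR | False claims |
|---|---|---|---|
| 40 months (SAP section 4) | 6% vs 3% | 0.995 | 2.4% |
| 40 months | 15% vs 5% | 0.981 | 2.9% |
| 100 months (assumed) | 6% vs 3% | 0.987 | 2.6% |
| 100 months | 15% vs 5% | 0.956 | 5.2% |
| 100 months | 15% vs 5%, half treatment-only | 0.976 | 3.4% |
| 100 months | 5% vs 15% | 1.045 | 0.6% |
| 100 months | 10% vs 10% | 0.998 | 2.1% |
| 100 months | 15% vs 5%, none treatment-only, no later deaths captured | 1.000 | 2.0% |

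In standard errors, ln(0.995) = −0.0050 is 0.05, ln(0.981) = −0.0192 is 0.18, and ln(0.956) = −0.0450 is 0.42. As a check on the table, Φ(−2.054 + 0.18) = 3.0% and Φ(−2.054 + 0.42) = 5.1%, close to the simulated 2.9% and 5.2%.

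A second simulation (2,000 runs per setting, 40-month median, withdrawal uniform over 0 to 36 months from randomization) gave 0.987 and 3.0% at 10% placebo versus 5% enzalutamide, and 0.975 and 3.8% at 15% versus 5%. With 10% placebo versus 20% enzalutamide and a true hazard ratio of 0.73, power fell from 80.8% to 70.3%.

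**4. Size on the sensible reading.** Censoring treatment-only survivors at their last contact gave hazard ratios of 0.996 to 1.001 and 1.9% to 2.2% false claims in every setting of the first simulation, where no deaths were recorded after withdrawal from follow-up.

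**The case for a change.** The best case for a change is that a favoured inference is not a specification. The bullet has no qualifier, Protocol 12.6.6 places treatment-only withdrawal under a general consent-withdrawal heading, and a programmer who took the recorded consent-withdrawal date at face value would get the wrong answer for these patients. The interim look had 84 deaths where Protocol 7.4.2 expected about 170, so the planning median may understate the effect and the 100-month rows may be the fairer guide. After unblinding the arms could well withdraw at different rates, and two added phrases would cost nothing.

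The text is indeed loose, and a misreading with a 10-point imbalance would not be trivial. Three things limit the point.

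- The misreading goes against the SAP's own use of the term and the stated aim of the section. The OS methods were set in the main-study SAP, which is not among the documents and may define the term.
- Tighter wording would not remove the asymmetry for a patient who withdraws from follow-up and whose death is learned of later, for instance through the secondary contacts in Protocol 2.2.1. Keeping every known death is a fair choice, and that residue comes with it.
- The obvious companion analysis, stopping deaths and survivors alike at withdrawal, is no safer. With a withdrawal-prone 15% in each arm at 2 or 3 times the hazard (assumed), and 5% placebo versus 15% enzalutamide withdrawing, it gave 0.969 (3.7% false claims) and 0.954 (5.3%). The literal reading of the current rule gave 1.031 (1.0%) and 1.022 (1.4%).

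**Conclusion.** This is a gap in detail that analysts would fill sensibly, and no change to the plan is called for. Read with SAP 3.2 and the rest of 6.1, the bullet covers withdrawal from survival follow-up; treatment-only withdrawers are censored at last contact, and the OS hazard ratio is essentially unaffected.

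Harm requires three things together: coding against that reading, mostly treatment-only withdrawal, and imbalance between arms. Under the assumed rates of 6% versus 3% to 15% versus 5%, the hazard ratio would then move by about 0.5% to 2% at the planning median, and by 1.3% to 4.4% at a 100-month median, in either direction. Because the documents give no withdrawal rates by type or arm, these figures show scale only and do not predict a bias. A note in the programming specification that only follow-up withdrawal ends OS observation would be harmless, but the validity of the OS test does not depend on it.
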